5.1.2.7 Visit 7 (+7 days from Visit 6): Endpoint

- *ADIS* sections for the anxiety disorder(s) the participant met criteria for at screening
- Rumination Response Scale (RRS)
- Hamilton Rating Scale for Depression (HAM-D)
- Hamilton Rating Scale for Anxiety (HAM-A)
- Generalized Anxiety Disorder 7-item Scale (GAD-7)
- Patient Health Questionnaire 9 (PHQ-9)
- The Temporal Experience of Pleasure Scale (TEPS)

Protocol # 1803019086
Version Date 12/27/2022

- Positive and Negative Affect Schedule (PANAS)
- Emotion Regulation Questionnaire (ERQ)
- Multidimensional Experiential Avoidance Questionnaire (MEAQ)

- Pittsburgh Sleep Quality Index (PSQI)
- World Health Organization Quality of Life short-form scale (WHOQOL-BREF)
- Life Events Scale for Students (LESS)
- Anxiety Sensitivity Index (ASI-3)
- Liebowitz Social Anxiety Scale (LSAS)
- Sensitivity to Punishment and Sensitivity to Reward Questionnaire (SPSRQ)
- Mobile Application Rating Scale: user version (uMARS)
- Digital Working Alliance Inventory (D-WAI)
- Optional MRI Tasks: Points Incentive Delay Task, Social Incentive Delay Task
- Optional EEG
- Medication Tracking
- Check in about how the app is working.

5.1.2.8 Visit 8 (+42 days from Visit 7): Follow-Up

- Rumination Response Scale (RRS)
- Hamilton Rating Scale for Depression (HAM-D)
- Hamilton Rating Scale for Anxiety (HAM-A)
- Generalized Anxiety Disorder 7-item Scale (GAD-7)
- Patient Health Questionnaire 9 (PHQ-9)
- The Temporal Experience of Pleasure Scale (TEPS)
- Positive and Negative Affect Schedule (PANAS)
- Emotion Regulation Questionnaire (ERQ)
- Multidimensional Experiential Avoidance Questionnaire (MEAQ)
- Pittsburgh Sleep Quality Index (PSQI)
- World Health Organization Quality of Life short-form scale (WHOQOL-BREF)
- Life Events Scale for Students (LESS)
- Anxiety Sensitivity Index (ASI-3)
- Liebowitz Social Anxiety Scale (LSAS)
- Sensitivity to Punishment and Sensitivity to Reward Questionnaire (SPSRQ)
- Mobile Application Rating Scale: user version (uMARS)
- Digital Working Alliance Inventory (D-WAI)
- Medication Tracking
- Check in about how the app is working.

5.2 Treatment Administration

Treatment will be administered on an *outpatient* basis.

Participants will be asked to engage with the mobile application at least 2 days a week

Protocol # 1803019086

Version Date 12/27/2022

for 20-25 minutes per session. These sessions can be done at the participants' convenience for various lengths of time. These tasks can be boring or frustrating for

some people, but participants are allowed to take breaks, or to make sessions shorter. Participants may also decide to stop participating at any time.

5.3 General Concomitant Medication and Supportive Care Guidelines

Participants will likely be seeking therapeutic services, medication-based as well as psychotherapy, outside of the research context for their anxious and depressed symptoms. This will be recorded by our protocol but will not interfere with their use of the mobile application. We do not foresee any possible risks associated with using the mobile application in addition to external non-CBT therapy.

5.4 Duration of Therapy and Criteria for Removal from Study

In the absence of treatment delays due to adverse event(s), treatment may continue for 12 weeks or until one of the following criteria applies:

The study will take place for a total of 6 weeks but participants will continue to have access to the mobile device if they would like to after the study is complete. Participants are welcome to withdraw from the study at their own discretion. There are no general or specific changes in the patient's condition that would render the patient unacceptable for further treatment in the judgement of the investigator.

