3.3 Exclusion Criteria

Individuals who do not meet the cutoff score on the ADIS or who have a primary diagnosis other than an anxiety disorder will be excluded from participating in this study. Additionally, participants who are currently in cognitive behavioral therapy outside of the app or who have changed their dose of a psychiatric medication in the past 12 weeks will be excluded. Participants with the intent or plan to attempt suicide will be excluded from this study and provided referrals for treatment.

4. Registration Procedures

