11.6 Reporting and Exclusions

Not applicable as we will not be using a drug or medical device.

12. Adverse Event Reporting Requirements

Adverse event (AE) monitoring and reporting is a routine part of every clinical trial. The investigator will be required to provide appropriate information concerning any findings that suggest significant hazards, contraindications, side effects, or precautions pertinent to the safe use of the drug or device under investigation. Safety will be monitored by evaluation of adverse events reported by patients or observed by investigators or research staff, as well as by other investigations such as clinical laboratory tests, x-rays, electrocardiographs, etc.

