12.2.4 AE/SAE Follow Up

Please specify any follow up procedures for any AEs/SAEs that occur on study. Sample language is provided below in *italics*.

All SAEs and AEs reported during this study will be followed until resolution or until the investigator confirms that the AE/SAE has stabilized and no more follow-up is required. This requirement indicates that follow-up may be required for some events after the patient discontinues participation from the study.

13. Data and Safety Monitoring Plan (DSMP)

- We will be using REDCap, a secure web application, to manage participant data. Only individuals listed as co-investigators on the protocol will have access to this database.
- All data that is collected by the study team will be stored in the REDCap database. All questionnaire data collected for the study (see attachment) will be stored in the REDCap system.
- Participants can discontinue engagement in the study at their own discretion. The only foreseeable adverse events that may cause subjects to terminate protocol treatment is that they may get tired or bored of the tasks they asked to engage in on the mobile application.
- The researchers will report all adverse events and unanticipated problems to the monitoring board as soon as they occur.
- The monitoring entity will review data/events annually with the continuing review for the study.
- The researchers will terminate the protocol if they receive information from the monitoring board that they should do so.
- The monitoring entity's comments/reviews will be disseminated during the continuing review.
- The study application (CBT App) environment is stored and processed on the Weill Cornell ITS server with analytics information sent to Heap Analytics, and text message communications via Way to Health. Data on IP address, phone carrier, and city, as well as use of the app is collected on these platforms.

These are companies outside of Weill Cornell that will have access to participants' personal information. If these data are further disclosed by them or their business partners, it may no longer be covered under the privacy protections. Text messaging does not provide a completely secure and confidential means of communication. Participants are made aware of the risks that are inherent in using text messaging.

References

Please provide the citations for all publications referenced in the text.

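### Section 5.4 rules out in advance any change in condition as a ground for stopping a participant's app use, and no supplied text carries the section 3.3 suicide-risk referral past enrolment

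*Combined protocol and SAP*

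**What the plan says.** Section 5.4 opens by announcing criteria for ending treatment: "In the absence of treatment delays due to adverse event(s), treatment may continue for 12 weeks or until one of the following criteria applies". No list follows. The section then gives one exit, "Participants are welcome to withdraw from the study at their own discretion", and goes on to recognise "no general or specific changes in the patient's condition that would render the patient unacceptable for further treatment in the judgement of the investigator".

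The only suicide-risk rule is in section 3.3: "Participants with the intent or plan to attempt suicide will be excluded from this study and provided referrals for treatment".

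General safety text appears in three places:

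- Section 12 (opening): "Safety will be monitored by evaluation of adverse events reported by patients or observed by investigators or research staff".
- Section 12.2.4: "All SAEs and AEs reported during this study will be followed until resolution or until the investigator confirms that the AE/SAE has stabilized".
- Section 13: "The researchers will report all adverse events and unanticipated problems to the monitoring board as soon as they occur", and "The researchers will terminate the protocol if they receive information from the monitoring board that they should do so".

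Section 12.1.2 says the program will cause no adverse events. Section 13 foresees only tiredness or boredom as adverse events that might lead a participant to stop.

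**The concern.** The 5.4 sentence is an affirmative rule, not silence. In the section meant to govern removal, it settles beforehand that no deterioration of any kind would make further treatment unacceptable in the investigator's judgement. The protocol nevertheless treats suicidal intent or plan at entry as a reason both to keep someone out and to refer them.

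What is at stake is the handling of a participant who enters eligible and worsens during the 6 weeks of treatment or by the follow-up visit 6 weeks later. Staff following the supplied text would evaluate, follow and report an adverse event. They would find no instruction to refer, and a statement that the person's condition cannot be a reason to stop. Continuing the app may often be the right decision, but it should be made case by case.

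**Working it through.** No arithmetic applies. The check sets the relevant sections side by side and asks two questions of each: does it give the investigator a ground for stopping one participant's app use, and does it provide a referral after enrolment?

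| Section | What it provides | Investigator ground to stop one participant? | Referral after enrolment? |
|---|---|---|---|
| 3.3 | Exclusion and referral for suicidal intent or plan | No, entry rule | No, entry rule |
| 5.4 | Voluntary withdrawal; passing mention of delays due to adverse events | No, expressly ruled out | No |
| 11.1 | Nobody is made to leave for low engagement | No, engagement only | No |
| 12 (opening) | Evaluation of adverse events | No | No |
| 12.1.2 | Expects no adverse events from the program | No | No |
| 12.2.4 | Follow-up to resolution or stabilisation | No | No |
| 13 | Reporting to the board; termination on its advice | No, termination is of the whole protocol | No |

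**Is 3.3 an entry rule?** Yes, on the better reading. It sits under section 3, Subject Selection, and section 3.1 ties the inclusion and exclusion criteria to eligibility. Another 3.3 criterion excludes people below the ADIS cutoff. Applied throughout, that would remove participants who improve, although ADIS sections are repeated at Visit 7. So 3.3 ends at enrolment, and its referral step ends with it.

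**Does the visit schedule close the gap?** Visits 2, 3, 4, 5, 6, 7 and 8 make 7 contacts after baseline. Each has the PHQ-9 and a check-in; the HAM-D is added at Visits 4, 7 and 8. The check-in is described only as concerning how the app is working. No text says who reviews the PHQ-9 or HAM-D, how soon, or what follows from a worrying answer. The contacts exist; the action does not.

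**Does outside care close it?** Only partly. Section 2.4 says existing therapies continue, and section 5.3 expects that participants will probably be seeking other services. But section 3.2 does not require outside care, and 3.3 excludes people currently in CBT elsewhere. Some participants may therefore have no treating clinician.

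**The case against.** The strongest reply is that continuing the app is a defensible choice. It supplements other care, participants may stop whenever they wish, and adverse events are evaluated, followed and reported. An entry rule and a continuation rule may properly differ: a state that bars someone from starting need not oblige them to stop. This stands. It means that continuing is not shown to be wrong, and that mandatory removal would be the wrong remedy. It does not explain why the protocol should decide the matter beforehand, or why the referral should lapse at enrolment.

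A reader might infer that 5.4 contradicts 3.3. That would follow only if 3.3 applied throughout the study, and its placement and its ADIS criterion make that reading implausible.

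A reader might also infer that participants have no individual exit, or that safety events go unassessed. Neither is right. Voluntary withdrawal is an individual exit, and sections 12 and 13 provide for evaluation, follow-up and reporting.

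Finally, part of the claim is an absence, and some material is out of view: the consent pages, the schema figure and the attachment mentioned in section 13. A referral procedure could be there. This limits confidence in the referral half of the point, but not in the reading of the 5.4 sentence.

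**Conclusion.** The point holds in two parts. First, with high confidence: 5.4 leaves no investigator-initiated ground for stopping one participant's app use, because it says that no change in condition would justify it. Second, subject to the material that could not be checked: no supplied passage carries the 3.3 referral past enrolment.

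No magnitude is claimed. The documents give no rate of new suicidal intent or plan, so the number of participants affected cannot be estimated from them. The conclusion rests on the text, on reading 3.3 as an entry rule, and on the judgement that a case-by-case decision is safer than one made in advance. It should be fixed because the remedy is cheap and uses the protocol's own referral step.

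**What to change.** Replace the 5.4 sentence with text to this effect:

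> The investigator may pause or stop app use for a participant whose condition worsens. A participant found to have intent or plan to attempt suicide at any visit after enrolment is clinically assessed and referred for treatment as in 3.3, and the investigator decides whether app use continues. Outcome assessments, including Visits 7 and 8, continue where the participant agrees.

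The first sentence is needed because 5.4 rules out every kind of deterioration, not only suicidality. The last separates stopping the app from leaving the study, which helps preserve the primary HAM-A comparison at Visit 7.

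Prompt the step through the existing check-in, with a direct question added, and through same-day staff review of the PHQ-9 (Visits 2 to 8) and the HAM-D (Visits 4, 7 and 8). Align section 12.1.2 and the section 13 sentence on tiredness or boredom, so that neither implies that clinical worsening cannot occur.

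Cost: amended text in three places, one question at 7 existing contacts, and no added visits. The real burden is operational: staff must review answers promptly, a clinician must be reachable, and phone or video visits need a working referral route.

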5.5 Duration of Follow Up

Patients will be followed for 6 weeks while they are participating in the study. There will also be a follow up appointment 6 weeks after they finish the study.

6. Dosing Delays/Dose Modifications

Section 6 is not applicable for this study as we are not administering a drug.

7. Pharmaceutical Information

This is not applicable for this study, as we are not administering a drug.

8. Correlative/Special Studies

Section 8 is not applicable for this study as there will be no correlative/special studies involving specimens.

9. Measurement of Effect

We will be measuring the effects of the mobile CBT program using clinical measures that test symptoms of anxiety and depression, namely, the Hamilton Rating Scale for Depression and the Hamilton Rating Scale for Anxiety. Optional fMRI scans will also be collected. The MRI scans will be done without contrast.

10. Data Reporting / Regulatory Considerations

10.1 Data Collection

The data collection plan for this study is to utilize REDCap to capture treatment, toxicity, efficacy, and adverse event data for all enrolled patients. All data collected from questionnaires will be kept in the “Mobile CBT” on Weill Cornell’s secure REDCap system. Additional data is stored on the Weill Cornell ITS servers, Way to Health Servers, and on Heap Analytics Servers.

10.1.1 REDCap

REDCap (Research Electronic Data Capture) is a free data management software system that is fully supported by the Weill-Cornell Medical Center CTSC. It is a tool for the creation of customized, secure data management systems that include Web-based data-entry forms, reporting tools, and a full array of security features including user and group based privileges, authentication using institution LDAP system, with a full audit trail of data manipulation and export procedures. REDCap is maintained on CTSC-owned servers that are backed up nightly and support encrypted (SSL-based) connections. Nationally, the software is developed, enhanced and supported through a multi-institutional consortium led by the Vanderbilt University CTSA.

10.1.2 Way to Health

Way to Health (W2H) is a software platform developed by the Penn Center for Health Incentives and Behavioral Economics (CHIBE) and is currently operated through a partnership between CHIBE and the Penn Medicine Center for Health Care Innovation. W2H is an integrated, cloud-based platform that blends behavioral science with scalable digital technology to improve clinical outcomes. W2H automates many research functions necessary for conducting randomized controlled trials of healthy behavior interventions. The platform facilitates online and mobile participant enrollment; survey administration; integrated biomedical device data transmissions; automated randomization in a variety of schemes; automated

communication with participants/patients via voice, text and email; delivery of financial and social incentives; utilization of gamification strategies and much more. For a complete list of data protections and associated policies and procedures, please visit <https://policy.waytohealth.org>.

10.1.3 Heap Analytics

Heap Analytics is a user behavioral analytics service that collects data on how users interact with websites and apps. Heap protects user privacy through automatic PII detection, custom install configurations, and a secure delete user API. All data sent to Heap is encrypted using TLS. For a full list of data protections and associated policies and procedures, please visit: <https://heap.io/trust-center>.

10.2 Regulatory Considerations

All protocol amendments and consent form modifications will be made by the Principal Investigator.

11. Statistical Considerations

As this study is a pilot to determine feasibility of the CBT mobile application including non-monetary incentives, we do not anticipate high volume data. We intend to use the pilot data to submit an NIH grant where we will recruit a statistician to be a part of our research team.

11.1 Study Design/Endpoints

No subjects will be forced to end participation in the study based on a lack of engagement with the mobile CBT program. We will be looking at whether participants completed the protocol as intended (i.e. usage statistics across the 6 weeks). We will gather the qualitative data from participants when they come for the weekly check-in visits. We will analyze how often participants opened the mobile app, completed the exercises and whether they completed the 6 week protocol, and if not, at what time point they stopped participating. We have no set criteria regarding what percentage must finish the protocol; however, if less than 25% of participants complete the protocol as intended, we will re-evaluate our current procedures. Such information is a critical first step *before* testing the validity of the mobile CBT platform, which will be the scope of future proposals to the NIH. We will also be comparing differences in efficacy and treatment engagement between three different incentive conditions. We will not be comparing the mobile CBT to any other type of treatment at this initial stage.

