11.2 Sample Size/Accrual Rate

We plan on recruiting 300 subjects over the course of a year, with the anticipation that 120 will participate in the study to completion. This means we hope to recruit approximately 25 subjects per month.

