11.4 Analysis of Endpoints

11.4.1 Analysis of Primary Endpoints

The primary purpose of the study is to compare change in anxious symptoms from baseline to Visit 7 (end of treatment with the mobile cognitive behavior mobile application) between the three incentive conditions. The primary measure of this endpoint will be the Hamilton Rating Scale for Anxiety (HAM-A), a 14-item questionnaire measure of the severity of anxiety symptoms. The items measure both psychic anxiety and somatic anxiety, where higher scores indicate a greater presence of symptoms and lower scores indicate mild to no anxiety symptoms. Secondary measures of this endpoint will be the Anxiety Sensitivity Index (ASI) and the Leibowitz Social Anxiety Scale (LSAS). The ASI is an 18-item scale containing three subscales measuring physical, cognitive, and social concerns regarding anxiety. Higher scores reflect greater self-reported concern and lower scores reflect little self-reported concern. The LSAS is a 24-item scale measuring fear and avoidance across social situations. Higher scores indicate greater fear and avoidance severity and lower scores indicate mild to no fear or avoidance.

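### Stopping the program is not separated from leaving the study, and nothing commits to a Visit 7 HAM-A from those who stop

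*Combined protocol and SAP*

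**What the plan says.** The primary aim in 11.4.1 is to "compare change in anxious symptoms from baseline to Visit 7" between the three incentive conditions, with the HAM-A as primary measure. Section 1.2 makes engagement with the program a secondary objective and hypothesises that social support may increase use.

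On people who stop, the protocol says the following.

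- **11.1:** "No subjects will be forced to end participation in the study based on a lack of engagement with the mobile CBT program". Completing as intended is explained there in terms of app usage. The same section will analyse app opening, exercise completion and "whether they completed the 6 week protocol, and if not, at what time point they stopped participating".
- **5.2 (treatment):** "Participants may also decide to stop participating at any time".
- **5.4 (duration of therapy and removal from study, under one heading):** "Participants are welcome to withdraw from the study at their own discretion".
- **13 (monitoring plan):** "Participants can discontinue engagement in the study at their own discretion". The next sentence speaks of ending protocol treatment and gives tiredness or boredom with the tasks as the only foreseen cause.
- **12.2.4:** adverse events are followed to resolution or stabilisation, if need be after a participant discontinues. No other follow-up after discontinuation is described.
- **11.2:** 300 are to be recruited "with the anticipation that 120 will participate in the study to completion".

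Visits 2 to 7 are scheduled by days since the previous visit, with no condition on app use, and may be held by phone or video (5.1.2). The HAM-A is taken at baseline and Visits 4, 7 and 8. Section 11.4.1 names endpoints and measures but no analysis set, model or missing-data method.

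**The concern.** There are two kinds of non-user. The passive one stops opening the app but says nothing; 11.1 means the team will not remove that person, and the visit schedule still applies. The active one tells staff that they want to stop. For that person the protocol describes only ceasing to participate or withdrawing. It does not tell staff to ask whether the person would still give the Visit 7 assessment.

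This matters more here than in most trials because the randomised factor is an incentive to keep using the program. If the arms work differently, the number who actively stop will differ by arm, and those who stop may well be those who are improving less. A comparison of the HAM-A among people still attending at Visit 7 would then no longer be protected by randomisation, and could favour the arm that loses more of its poor responders. The uMARS at the end of treatment is exposed in the same way, since people who disliked the program and left would not rate it then. Only that rating is affected, because the uMARS is also collected at Visits 2 and 4.

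**Working it through.** **1. What the plan's own figures give.** Accrual: 300 / 12 months = 25 per month, which agrees with 11.2. Completion: 120 / 300 = 40%. If all 300 were randomised, 60% would not complete. The protocol summary, however, calls 300 the screening ceiling and 120 the sample size; if 120 are randomised and 120 complete, the loss is 0%. Expected loss after randomisation therefore lies anywhere from 0% to 60% and cannot be fixed from the documents. No share stopping the program, no share missing Visit 7 and no HAM-A standard deviation is given.

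**2. The passages side by side.**

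| Question | Answer in the protocol |
|---|---|
| Is a participant removed for low use? | No (11.1) |
| Does Visit 7 depend on use? | No condition stated (5.1.2) |
| Is stopping the program defined apart from withdrawal? | No (5.2, 5.4, 13) |
| Is the Visit 7 HAM-A sought after an active stop? | Not stated |
| Who enters the primary comparison? | Not stated (11.4.1) |

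The first two answers protect passive non-users. The last three leave active stoppers, and the analysis, open.

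**3. Hypothetical bias in HAM-A points.** Let *s* be the proportion of an arm that stops, and *g* the completer mean minus the stopper mean of HAM-A change. The arm mean is (1 − *s*) × completer mean + *s* × stopper mean, so

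completer mean − full-arm mean = *s* × *g*.

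With the same *g* in both arms, a completers' contrast is off by (*s*₁ − *s*₂) × *g*. Assumptions, none from the documents: stopping of 40% and 20%, and every stopper missing Visit 7.

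| Assumed gap *g* (points) | (0.40 − 0.20) × *g* |
|---|---|
| 3 | 0.6 |
| 5 | 1.0 |
| 8 | 1.6 |

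With equal stopping, or no gap, the bias is 0. If some stoppers still attend Visit 7, it is generally smaller.

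**4. A second hypothetical, in SD units.** A simulation took completion rates 20 percentage points apart (80% v 60%, 70% v 50%, 50% v 30%), a correlation of 0.3 or 0.5 between HAM-A improvement and an underlying tendency to complete, and no true difference between arms. The completers' contrast was off by 0.09 to 0.11 SD at correlation 0.3 and by 0.15 to 0.18 SD at 0.5, in favour of the arm with fewer completers.

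**5. Precision.** Assume 120 randomised 1:1:1, two-sided 5%, 80% power and one pairwise contrast. The detectable difference is √(2/*n*) × (1.96 + 0.84) SD: 0.63 SD with 40 per arm, 0.70 with 32 (20% lost) and 0.81 with 24 (40% lost).

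**The case against.** The strongest reply is that 11.1 rules out the problem: nobody is forced out for lack of engagement, visits are timed without regard to use, phone and video are allowed, and 5.2 lets a bored participant take breaks or shorten sessions. On this view the words about when people stopped are part of a descriptive usage outcome and set no discontinuation rule. Much of this stands. A reader might infer that the protocol equates stopping the app with leaving the study, that the Visit 7 HAM-A is therefore lost, and that the primary analysis is of completers. The documents do not support any of these. No text skips Visit 7 for someone who stops, and 11.4.1 does not restrict the analysis. The figure of 120 in 11.2 is an accrual expectation and sets no analysis population.

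Nor should the 25% threshold in 11.1 be read as a tolerance for missing outcomes. It concerns completing as intended, which that section explains by usage.

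It is also fair that some data will exist for early stoppers: the HAM-A at Visit 4, the GAD-7 at every visit from baseline until they leave, and the uMARS at Visits 2 and 4, for those who stay that long. These help but do not replace the Visit 7 value.

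What the reply does not answer is the active stopper. A rule against forced removal says nothing about what staff should ask of a person who chooses to stop. The pilot setting does not excuse the gap either: the arm comparison is the stated primary purpose, and section 11 defers recruiting a statistician to a later grant, so one cannot assume the gap will be filled sensibly during analysis.

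**Conclusion.** The point holds as an unstated follow-up rule combined with an unstated analysis set. The protocol retains passive non-users but neither separates actively stopping the program from withdrawing nor commits to the Visit 7 HAM-A afterwards. In a trial whose arms are meant to change engagement, that outcome may be missing selectively by arm and by response, and nothing written prevents a completers' comparison.

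The size is unknown. The 0.6 to 1.6 HAM-A points and the 0.09 to 0.18 SD show what could happen under assumed stopping rates, gaps and correlations; neither range estimates what will happen in this trial. The plan should be changed because an uncollected outcome cannot be recovered later and modelling from interim visits can only partly repair the loss.

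**What to change.** **Section 5.4 (with 5.2 and 13 brought into line).** Define two events, stopping use of the program and withdrawing consent to further contact, and record the date of each. Ask everyone who stops the program but has not withdrawn consent for the Visit 7 HAM-A, with ASI-3, LSAS and uMARS, at its scheduled time (six intervals of 7 days, so day 42 from Visit 1) by phone or video, and for Visit 8.

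**Section 11.4.1.** State that all randomised participants are analysed in their assigned arm, using Visit 7 data whether or not the program was still in use. Use the Visit 4 HAM-A to help handle values still missing, for example in a mixed model with baseline, Visit 4 and Visit 7, and add a sensitivity analysis that allows missingness to depend on the unseen value. Report Visit 7 completeness by arm.

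**Section 11.2 and the summary.** Reconcile whether 300 are screened or enrolled, and whether 120 are randomised or complete.

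**Cost.** An amendment, consent wording and some extra calls within the existing schedule. The estimated differences between arms will include people who stopped the program and may be smaller.
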